4.5. Safety Parameters

The safety parameters include AEs, clinical laboratory tests, vital sign measurements, and physical examination.

4.5.1. Adverse Events

AE verbatim terms as reported by the investigator will be mapped to System Organ Class and Preferred Term (PT) using the Medical Dictionary for Regulatory Activities (MedDRA) Version 19.0.

4.5.1.1. Treatment Emergent Adverse Events

TEAEs are defined as any AEs that occur or worsen (increase in severity) after treatment initiation through the 14-day follow-up period.

Refer to Section 6.3.1.1 to identify TEAE status when start date of an AE is unknown.

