8.1.5. Single-dose Phase

The open-label, single-dose phase will use oxymorphone HCl immediate-release oral liquid (Groups A and B) or oxymorphone HCl IV (Groups C and D) for PK assessments and to determine which dose (for each age group) to take forward into the multiple-dose phase (Figure 1). For each age group, up to 3 cohorts of 5 subjects will receive oxymorphone HCl (either immediate release oral liquid or IV, based on age. Subjects in Groups A and B must be able to tolerate oral intake prior to receiving oxymorphone oral liquid. Once the subject's analgesic regimen has been discontinued per standard of care, baseline assessments will be collected as documented in Table 3 and Section 8.1.3. All subjects will then be closely monitored for pain and their pain score will be recorded at least hourly until their pain score is ≥ 4 on the FLACC or ≥ 3 on the NIPS, at which time baseline dosing assessments will be performed and they will be administered study drug. The FLACC will be used for subjects in Group A and Group B. The NIPS will be used for subjects in Group C and Group D. Morphine-NCA per SOC (section 8.1.4) will be initiated coincident but not earlier than the first study drug administration. Bolus morphine administration may be given per standard of care. No food or oral liquid restrictions will be imposed around the time of dosing. All subjects will receive rescue by morphine-NCA as needed. Non-opioid analgesics (acetaminophen and/or non-steroidal anti-inflammatory drugs [NSAIDs] per SOC may be used to treat breakthrough pain not earlier than 6 hours following administration of study drug.

• Subjects will undergo subsequent pain assessments as noted in Table 3. All pain assessments will be conducted using an age-appropriate pain instrument (FLACC or NIPS). PK and additional assessments will occur at fixed intervals throughout the single-dose phase, as outlined in Table 3. Food consumption will be recorded from the period 1 hour prior to administration of study drug through EOT assessment; record all times that any food was consumed and what food was consumed (DAT, DAT-soft, FF, CF, water, formula, breast milk). The following assessments are to be completed during the single-dose phase.

Following administration of study drug, procedures and assessments will include the following:

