8.1.7. End-of-treatment/Early Termination

At the completion of the single- or multiple-dose phases, EOT assessments and procedures will occur at 24 hours after the last study drug administration or upon early study withdrawal. Each subject will be required to complete all EOT/ET assessments and procedures unless consent has been withdrawn. EOT assessments will include:

- Ongoing collection of AEs/SAEs (section 12).

- Performing physical examination: a brief physical examination, excluding length and weight, to assess the subject's overall health and physical status.
- Measuring vital sign (section 12.8).
- For the single-dose phase, collecting a blood sample for PK assessments (at 24 hours or upon EOT, if possible).
- For multi-dose phase, no blood sample for PK assessments will be drawn at EOT.
- Obtaining clinical laboratory tests (section 12.7): clinical laboratory tests as part of SOC will be acceptable.
- Assessing respiratory and neurological function (section 12.10, section 12.11 and Appendix A).
- Telemetry and pulse oximetry will be ongoing to EOT or ET.
- Updating and recording concomitant medications (including NCA rescue medications).
- Pain assessment (FLACC or NIPS; Appendix C or Appendix D, respectively) will be recorded.
- Recording of food consumption from the period 1 hour prior to administration of study drug through EOT assessment; record all times that any food was consumed and what food was consumed (DAT, DAT-soft, FF, CF, water, formula, breast milk).
- Converting subjects to a marketed opioid upon discharge, if required.
- Scheduling the 3-day and 14-day follow-up telephone call: assessment to include ongoing or new AEs, SAEs, and associated concomitant medications. The complete Schedule of Events is provided in Table 3 and Table 4

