12. ASSESSMENT OF SAFETY

12.1. Definitions

12.1.1. Adverse Events

An adverse event (AE) is any unfavorable or unintended change in body structure (signs), body function (symptoms), laboratory result (eg, chemistry, EKG, X-ray, etc.), or worsening of a pre-existing condition associated temporally with the use of the study medication whether or not considered related to the study medication. AEs will be captured once a subject has signed the informed consent. AEs include:

- Changes in the general condition of the subject
- Subjective symptoms offered by or elicited from the subject
- Objective signs observed by the Investigator or other study personnel
- All concurrent diseases that occur after the start of the study, including any change in severity or frequency of pre-existing disease. Post-operative pain should be captured as an AE after the EOT.
- All clinically relevant laboratory abnormalities or physical findings that occur during the study

A treatment-emergent adverse event (TEAE) is any condition that was not present prior to treatment with study medication but appeared following treatment, was present at treatment initiation but worsened during treatment, or was present at treatment initiation but resolved and then reappeared while the individual was on treatment (regardless of the intensity of the AE when the treatment was initiated).

All AEs, including observed or volunteered problems, complaints, signs or symptoms must be recorded on the AE page of the eCRF, regardless of whether associated with the use of study medication. This would include AEs resulting from concurrent illness, reactions to concurrent medication use, or progression of disease states (excluding the disease under study). A condition present at baseline that worsens after initiation of study treatment will be captured as an AE; the onset date will be the date the event worsened. The AE should be recorded in standard medical terminology when possible.

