12.4. Intensity Assessment

The intensity (or severity) of AEs is characterized as mild, moderate, or severe:

- **Mild** AEs are usually transient, requiring no special treatment, and do not interfere with the subject's daily activities.
- **Moderate** AEs introduce a low level of inconvenience or concern to the subject and may interfere with daily activities, but are usually ameliorated by simple therapeutic measures.
- **Severe** AEs interrupt a subject's usual daily activity and typically require systemic drug therapy or other treatment.

When the intensity category of an AE changes, the greatest intensity during that continuous episode should be recorded.

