14.6.3. Adverse Events

The Medical Dictionary for Regulatory Activities (MedDRA) will be used to code AEs.

An AE (classified by preferred term) that started during the treatment period will be considered a TEAE if it was not present prior to the first dose of study drug, or was present prior to the first dose of study drug but increased in intensity during the treatment period. If more than 1 AE is reported prior to the first dose of study drug and coded to the same preferred term, then the AE with the greatest intensity will be used as the benchmark for comparison to the AEs occurring during the treatment period which were also coded to that preferred term. Any AE present prior to the first dose of study drug that increases in intensity during the treatment period will be re-entered with a new start date of the date of increased intensity. An AE that occurs more than 14 days or 5 half-lives, whichever is longer, after the last dose of study drug will not be counted as a TEAE.

Descriptive statistics (the number and percentage) for subjects reporting TEAEs will be tabulated by system organ class and preferred term; by system organ class, preferred term, and severity; and by system organ class, preferred term, and relationship to study drug. If more than 1 AE is coded to the same preferred term for the same subject, the subject will be counted only once for that preferred term using the most severe and most related occurrence for the summarization by severity and by relationship to the study drug.

The distribution of TEAEs by severity and relationship to study drug will be summarized. SAEs and AEs leading to premature discontinuation of study drug will be summarized by preferred term and treatment group, and sorted by decreasing frequency for the test treatment. SAEs will be displayed separately for those events occurring before the first study drug dosing date and all subsequent ones.

These tabulations will be stratified by age group and dose group for the single-dose phase and treatment group for the multiple-dose phase.

Listings will be presented for subjects with SAEs, subjects with AEs leading to discontinuation, and subjects who die (if any).

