3.8.1. Adverse Events Definitions

An AE was any unfavorable or unintended change in body structure (signs), body function (symptoms), laboratory result (e.g., chemistry, ECG, X-ray, etc.), or worsening of a pre-existing condition associated temporally with the use of the study drug whether or not considered related to the study medication. AEs include:

- Changes occurred in the general condition of the subject.
- Subjective symptoms offered by or elicited from the subject.
- Objective signs observed by the investigator or other study personnel.
- All concurrent diseases that occurred after the start of the study, which included any change in severity or frequency of pre-existing disease. Post-operative pain was captured as an AE after the EOT.
- All clinically relevant laboratory abnormalities or physical findings that occurred during the study.

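### The SAP's TEAE definition leaves out the protocol's test for a pre-existing condition, so continuing postoperative pain recorded after EOT can count as treatment-emergent

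*SAP*

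**What the plan says.** - **Entry condition.** Protocol 8.1.5 withholds study drug until "their pain score is ≥ 4 on the FLACC or ≥ 3 on the NIPS". Protocol 8.1.3 and 8.1.6 set the same threshold.
- **When pain becomes an AE.** Protocol 12.1.1: "Post-operative pain should be captured as an AE after the EOT". SAP 3.8.1 repeats it in the past tense: "Post-operative pain was captured as an AE after the EOT".
- **When EOT falls.** Protocol 8.1.7: "EOT assessments and procedures will occur at 24 hours after the last study drug administration or upon early study withdrawal". In an infant who leaves early, pain becomes recordable sooner.
- **TEAE in the SAP.** Section 4.5.1.1: "TEAEs are defined as any AEs that occur or worsen (increase in severity) after treatment initiation through the 14-day follow-up period". There is no exception for the condition under treatment.
- **TEAE in the protocol.** Section 12.1.1 defines it by condition: "any condition that was not present prior to treatment with study medication but appeared following treatment", or one that was present and worsened, or one that resolved and came back on treatment. Section 14.6.3 works by preferred term. An AE starting in the treatment period qualifies if "it was not present prior to the first dose of study drug", or if it was present then and became more intense.
- **Outputs.** SAP 7.8.2 bases the AE summary tables on TEAEs unless stated otherwise. Its overview shows total TEAEs, totals by severity, and the number of subjects with a related or a severe TEAE.
- **Blank fields.** SAP 4.5.1.2 imputes missing severity as the most severe grade. SAP 4.5.1.3 treats missing relationship as related. SAP 6.3.1.1 counts an AE of unknown onset as a TEAE if it is ongoing or ended on or after the first dose.
- **Declared changes.** SAP section 8 lists only the removal of the efficacy and PK analyses.

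**The concern.** Pain is the condition being treated. Up to EOT it is handled as such, and afterwards the same pain may enter the AE database. Because no pain AE is captured before EOT, no earlier AE record exists to mark it as pre-existing. A definition that asks only whether an AE occurred after treatment initiation then has nothing to screen it out.

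The abbreviated report is confined to safety, so the TEAE tables are among its main results. If surgical pain sits in the aggregate lines, those lines partly describe the surgery rather than the drug. The single-dose phase is summarised by age group and dose group, so the denominators are very small and a single record is visible in a percentage.

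**Working it through.** The plan states no expected TEAE rate, so there is no figure to reproduce. The check sets the definitions side by side and then shows how far one record can move a count.

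**Step 1. Which post-EOT pain records count?**

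| Post-EOT pain record | SAP 4.5.1.1 | Protocol 12.1.1 |
|---|---|---|
| Unchanged pain, onset dated before first dose | Not a TEAE | Not a TEAE |
| Unchanged pain, onset dated after EOT | TEAE | Not a TEAE: condition already present |
| Pain reported as worsened | TEAE | TEAE, if the worsening counts as during treatment |
| Pain resolved, then recurred | TEAE | TEAE, if the recurrence counts as on treatment |
| Onset unknown, ongoing or ended on or after first dose | TEAE (SAP 6.3.1.1) | Not a TEAE unless worsened or recurred |

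The clear conflicts are in the second and last rows. Protocol 12.1.1 dates a worsened baseline condition to the day it worsened. Neither document says what onset date to give pain that simply continues past EOT.

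Protocol 14.6.3 does not settle the matter. Its benchmark is an AE reported before the first dose under the same preferred term, and under the capture rule pain has no such record.

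**Step 2. What can one record do?** An infant whose only TEAE is post-EOT pain adds 100/n percentage points to the share of infants with any TEAE:

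- n = 5 (one cohort; SAP 3.1 reports 5 infants enrolled in Group B): 100/5 = 20 points
- n = 10: 10 points
- n = 15 (three cohorts pooled): 6.7 points

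The overview list in SAP 7.8.2 does not name a row for subjects with any TEAE. The table layouts are in a separate module. The total number of TEAEs rises by one per record in any case.

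**Step 3. Illustration with assumed rates.** Let p0 be the TEAE rate without postoperative pain and q the share of infants with a counted pain record, independent of each other. Neither value is in the documents.

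Observed rate = 1 − (1 − p0)(1 − q)

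- p0 = 40%: q = 10% gives 1 − 0.6 × 0.9 = 46%; q = 20% gives 52%; q = 40% gives 64%; q = 60% gives 76%.
- p0 = 20%, q = 10%: 1 − 0.8 × 0.9 = 28%.

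For severe TEAEs, replace q by q × s, where s is the share of those records graded severe. With an assumed base of 5% and q = 60%:

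- s = 0: 5%, no change
- s = 10%: 1 − 0.95 × 0.94 = 10.7%
- s = 30%: 1 − 0.95 × 0.82 = 22.1%

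**Step 4. Two arms.** If the same q applies to both multiple-dose arms, a difference narrows. Assumed rates of 60% and 30% at q = 40% become 1 − 0.4 × 0.6 = 76% and 1 − 0.7 × 0.6 = 58%, so 30 points shrink to 18.

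**The case against.** The strongest reply concerns the capture rule itself. The pain sentence closes a bullet on changes in severity or frequency of pre-existing disease, and the protocol's summary of changes says it was added to tell sites when worsening of an existing condition should be documented. Protocol 12.1.1 also leaves the disease under study out when it speaks of progression. On that reading sites record only pain that worsens after EOT, and such a record would generally qualify under either definition. This reading is fair, but the sentence as written is not limited to worsening, so the gap remains.

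A reader might infer three stronger things that the documents do not support:

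- **That severe-TEAE counts are inflated.** Protocol 12.4 says severe AEs "typically require systemic drug therapy or other treatment", and analgesics are allowed after EOT. But the same definition also requires that usual activity be interrupted. Analgesic use alone does not make pain severe.
- **That the drug signal is hidden.** TEAEs are tabulated by system organ class and preferred term and listed by subject (SAP 7.8.2), so pain has its own rows. Vital signs with oxygen saturation, apnea and sedation are summarised separately (SAP 7.8.5 and 7.9.1). Only the aggregate lines can blur. SAP 7.8.2 plans no test between arms.
- **That protocol 14.6.3 would exclude the record.** It might not, because its benchmark is a pre-dose AE record.

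**Conclusion.** The point holds as a gap in definition and display. SAP 4.5.1.1 omits the condition-based test of protocol 12.1.1 without saying so. Continuing surgical pain entered with a post-EOT or unknown onset can therefore count as treatment-emergent. It can inflate the aggregate TEAE counts. It reaches the severe or related counts only if it is graded that way or if those fields are missing.

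A reader might infer that nearly every infant acquires a TEAE this way, since all had pain at dosing. That does not follow: pain dated to surgery and not worsened is not counted, and sites may have recorded only worsening. The size cannot be derived from the documents. The firm figure is the leverage of one record, 20 points in a cohort of 5. The other rates rest on assumed values of p0, q and s and on independence, and they start as low as a 6-point rise (40% to 46%).

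**What to change.** 1. In SAP 4.5.1.1, restore the condition-based definition of protocol 12.1.1. Treat postoperative or procedural pain as pre-existing in every dosed infant, and not treatment-emergent unless reported as worsened or as resolved and recurred. State that the existing 14-day window applies to worsening and recurrence. If the present wording is kept instead, declare the departure in SAP section 8.
2. In SAP 7.8.2, show the overall, by-severity and related TEAE counts with and without postoperative and procedural pain preferred terms. Fix the list of terms before database lock.
3. List post-EOT pain records separately, with onset date, severity and relationship as reported, so that imputed values can be seen.

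Do not make the rule depend on a comparison with the pre-dose FLACC or NIPS score. No pain score is scheduled after EOT, and the documents do not map those scores to AE grades.

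All of this uses data already collected. The cost is a short wording change, one listing and a few extra summary rows. The paired rows remain informative whatever onset dates the sites used.

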4.5.1.2. Intensity of Adverse Events

Intensity (or severity) of AEs were be graded as “Mild”, “Moderate” or “Severe”. For AEs with missing severity, the most severe assessment will be imputed for analyses, following worst case principle. If the intensity of an AE changes, then the most severe intensity during the continuous episode will be recorded.

4.5.1.3. Relationship to Study Drug

The causal relationship with study drug was classified by the investigator and were reported as follows:

- Not related.
- Unlikely related.
- Possibly related.
- Probably related.

Related adverse events are AEs with the relationship described by the investigator as “probably related” or “possibly related”. “Not related” or “Unlikely related” causality assessments are considered as not related.

“Probable” and “Possible” causality assessments will be considered as positive causality. “Not” and “Unlikely” causality assessments will be considered as negative causality.

Any missing relationship of an AE to study drug will be considered as related to study drug for the analyses, following worst case principle.

4.6. Other Safety Parameters

4.6.1. Respiratory and Neurological Function

All subjects were monitored for the appearance of respiratory and neurological symptoms.

Respiratory functions:

- Monitoring of oxygen saturation at the time of vital sign assessments
- Apnea monitoring
 - Were any episodes of apnea observed?
 - If apnea observed, was the episode considered to be an AE?

Neurological functions:

- Monitoring the level of sedation through Modified Ramsay Sedation Scale
 - Was sedation considered as an adverse event?
- Interpretation of Modified Ramsay Sedation Scale scores:
 - Score 2-3: Anxiolysis
 - Score 4-5: Moderate sedation
 - Score 6: Deep sedation
 - Score 7-8: General anesthesia

5. ANALYSIS POPULATIONS

This study was terminated early. Baseline assessments and safety assessments will be summarized using the Safety Population. Table 7 describes the analysis populations used to describe safety assessments in this study.

Table 7: Analysis Populations

Population	Definition	Displays
Single-Dose Safety Population	The Safety Population of the single-dose phase includes all subjects who receive at least 1 dose of study drug in the single-dose phase.	All safety analyses and demographic/baseline characterization for the single-dose phase will use this population.
Multiple-Dose Safety Population	The Safety Population of the multiple-dose phase includes all subjects who receive at least 1 dose of study drug or placebo in the multiple-dose phase. Subjects will be attributed to the treatment that they actually received regardless of their assigned randomized treatment.	All safety analyses and demographic/baseline characterization for the multiple-dose phase will use this population.
Overall Safety Population	Includes all the subjects in the Single-dose Safety Population and the Multiple-dose Safety Population	All the subject listings except disposition listings will use this population. Disposition will be based on all subjects enrolled.

6. STATISTICAL METHODS

6.1. General Methodology

All statistical tests, summary tables and data listings will be prepared using SAS version 9.4.

Continuous data will be summarized using descriptive statistics. Discrete data will be summarized using frequency counts and percentages. The denominator will be based on the number of evaluable subjects in the appropriate population.

For the purpose of display, the summary results will be rounded as follows:

- Minimum and maximum: same number of decimal places as the raw data.
- Mean and Median: one decimal place more than the raw data.
- Standard deviation (SD): Two decimal places more than the raw data.
- Percentages will be displayed with one decimal place precision.

For categorical variables with missing values, a category documenting the frequency of missing values will be displayed in the summary tables.

Summary tables, subject listings, graphs and any supportive SAS output will include footnotes that will indicate:

- Date of data extraction.
- Date and time of output generation.
- SAS program name, including the path, which generated the output.

When calculating percentages, the denominator will be based on the number of subjects with non-missing values. If the denominator is expected to change over time, then the denominator used to calculate the percentage will be based on the number of subjects with non-missing values at each visit.

Summary tables and data listings without values will be presented with a note stating that “No Subjects Met Criteria”.

Subject listings of all data from the eCRFs as well as any derived variables will be presented.

